## Background and Rationale

Doxorubicin, an inhibitor of DNA topoisomerase 2a (Top2a), is routinely used in the treatment of breast cancer, sarcoma, and pediatric leukemia. Long-term cancer survivors who were treated with doxorubicin often suffer from dose-dependent cardiotoxicity. Of the two topoisomerase 2 isozymes, Top2a is highly expressed in cancer cells and is required for cell division. However, adult cardiomyocytes express only topoisomerase 2b(Top2b). Studies from our laboratory showed that **Top2a mediates doxorubicin's tumoricidal activity, whereas Top2b mediates doxorubicin's cardiotoxic effect**. At present, dexrazoxane is the only FDA-approved drug for cardio- protection. The cardio- protective effect of dexrazoxane is due to its ability to bind to the ATPase domain of Top2b to inhibit Top2b's catalytic cycle. Currently, dexrazoxane is administered concurrently with doxorubicin. The FDA recommended dose of Dexrazoxane is 10 times the dose of Doxorubicin. Because dexrazoxane also binds to Top2a, it has the potential to interfere with doxorubicin's tumoricidal effect. Thus, dexrazoxane has limited clinical utility as specified by FDA's approved indication. In preliminary studies, **dexrazoxane induced an ubiquitin/proteasome-mediated degradation of Top2b, but not Top2a. By administering dexrazoxane eight hours before doxorubicin, Top2b will be degraded to avoid cardiotoxicity, whereas Top2a will remain intact to preserve tumoricidal efficacy**. Because the half-life of dexrazoxane is two hours, 93.75% of dexrazoxane will be eliminated eight hours (four half-lives) after administration. Indeed, dexrazoxane pre-treatment eight hours before doxorubicin provided complete protection against doxorubicin-induced cardiotoxicity in our animal model. We propose to conduct an investigator-initiated clinical trial to test this hypothesis. We will use the results from this study to design a pilot clinical trial on breast cancer patients.

## Objectives

**Primary Objective:** To determine the effective dose of Dexrazoxane pre-treatment in degrading topoisomerase 2 b (Top2b) in human peripheral blood.

**Secondary Objectives:** To determine the time course of Top2b degradation in healthy human volunteers. To determine topoisomerase 2 a (Top2a) in human peripheral blood will not be degraded by Dexrazoxane

## Study Design and Procedures

This is a Phase 1 trial to determine time course and dose of dexrazoxane pre-treatment for optimal degradation of Topoisomerase 2 b (Top2b) in human volunteers. The FDA recommended dose of Dexrazoxane is 10 times the dose of Doxorubicin. All the doses in this protocol are in the FDA approved range and have been prescribed for many years.

There will be 5 cohorts for different doses: 100mg/m^2, 200 mg/m^2, 300 mg/m^2, 400 mg/m^2, or 500 mg/m^2. Our plan is to enroll up to 5 subjects per cohort. We will start with 100 mg/m^2 and analyze the Top2 protein level from up to five subjects. Doses will escalate to

200 mg/m^2, 300 mg/m^2, 400 mg/m^2, and 500 mg/m^2. If 100 mg/m^2 dexrazoxane is insufficient, we will increase the dose to find the optimal dose.

A blood sample will be obtained at screening to rule out anemia, pregnancy and to determine liver and kidney functions. If the serum pregnancy test is not performed at the time of the initial screening blood draw and another attempt is required in order to perform this test, a urine pregnancy test can be used as a substitute. A urine pregnancy test will be done on the day of the 12-hour infusion visit, prior to infusion.

Subjects will be administered a dose of dexrazoxane by IV infusion over 15 (+/- 5) minutes.

Blood will be drawn to purify peripheral blood leukocytes for Top2b and Top2a assessment using Western blot analysis. 20 mL of blood will be drawn before dexrazoxane infusion. 10 mL of blood will be drawn hourly (+/- 5 minutes) after the start of infusion for 12 hours. The final lab draw of the 12-hour infusion day may occur at 6:30 pm based on facility and staff availability. The final blood draws occur at 24 hours (+/- 2 hours); and 48 hours (+/- 2 hours) from the start of infusion. A total of 17 blood samples will be drawn for each subject.

Subjects will be screened for COVID at each visit per institutional standards. Subjects who do not pass the screening will not be permitted to continue with the study.

Vital signs will be recorded at the following time points: 1) screening, 2) pre-infusion, 3) end of infusion, 4) 6 hours post-infusion, 5) 12-hours post infusion/discharge. Vital signs to be captured include: heartrate; respirations; blood pressure; temperature; pain (rate pain on scale of 1-10). Height and Weight will also be recorded at screening.

A parking voucher will be provided for each visit. During the first 12 hours after infusion, meals and a parking voucher will be provided.

Each subject will have a safety CBC one week (+/- 2 days) after dexrazoxane infusion to rule out myelosuppression. If the one-week post-study blood counts are below normal range, subject will have additional CBC two weeks post-infusion.

Treatment failure and subject removal criteria includes: subject noncompliance with blood draw, or, subject develops rare hypersensitivity reactions to dexrazoxane infusion.

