### **Data Analysis**

The goal of this protocol is to find the effective dose of dexrazoxane in degrading Top2b for the subsequent randomized clinical trial. We will select a dose of dexrazoxane, which reduces Top2b to less than 5% of baseline level in 8 hours in 5 volunteers. FDA recommended dose of dexrazoxane is 10 times the dose of doxorubicin. In the attached FDA approval documentation of dexrazoxane, 500mg/m^2 is cited as a recommended dose. We will study dose levels 500mg/m^2 or below. Healthy volunteers will be administered a dose of dexrazoxane. Blood will be drawn to purify peripheral blood leukocytes for Top2b and Top2a assessment using Western blot analysis. The following time points will be assessed: Pre-infusion, 1, 2, 3, 4, 5, 6, 7, 8, 9, 10, 11, 12, 24, and 48 hours after start of dexrazoxane infusion. Each dose level will be administered to up to five subjects, starting with an initial dose of 100 mg/m^2, and escalating in 100 mg increments.

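### Does allowing the last infusion-day draw at 6:30 pm spoil the 12-hour point of the Top2b time course?

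*Protocol*

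**What the plan says.** The Study Design and Procedures section of the protocol sets the sampling rule for the infusion day: "10 mL of blood will be drawn hourly (+/- 5 minutes) after the start of infusion for 12 hours". The next sentence relaxes it for one sample: "The final lab draw of the 12-hour infusion day may occur at 6:30 pm based on facility and staff availability". The two later samples have their own window: "The final blood draws occur at 24 hours (+/- 2 hours); and 48 hours (+/- 2 hours) from the start of infusion". The same section gives a count: "A total of 17 blood samples will be drawn for each subject".

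The Data Analysis section lists the times to be assessed: "Pre-infusion, 1, 2, 3, 4, 5, 6, 7, 8, 9, 10, 11, 12, 24, and 48 hours after start of dexrazoxane infusion". It attaches no tolerance to any of them. It also gives the dose-selection criterion, a dose that "reduces Top2b to less than 5% of baseline level in 8 hours in 5 volunteers".

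The objective that draws on the whole curve is secondary (Objectives): "To determine the time course of Top2b degradation in healthy human volunteers".

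The protocol gives no time of day for the start of infusion.

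**The concern.** Every other timing allowance in the sampling schedule is measured from the start of infusion. This one is a time on the clock. Without a fixed start, a 6:30 pm sample has no fixed elapsed time, so it may be labelled 12 hours without having been taken at 12 hours. The Data Analysis list, read alone, promises a 12-hour value for every subject.

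Two things would be at stake. First, the 12-hour sample is the last one before a gap to about 24 hours. With up to five subjects per cohort, one or two mistimed samples could move a cohort's nominal 12-hour value. Second, if the allowance were used after a late morning start, 6:30 pm would coincide with the 11-hour draw or come before it. Hourly points could then be lost, not merely shifted.

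**Working it through.** **Inputs** (Study Design and Procedures unless stated): hourly draws 1 to 12 from the start of infusion, +/- 5 minutes; last infusion-day draw permitted at 18:30; later draws at 24 and 48 hours, +/- 2 hours; 17 samples per subject; dose-selection time 8 hours (Data Analysis). The start time is not stated, so it is varied as an assumption.

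**1. The plan's own count.** Top2 samples: 1 pre-infusion + 12 hourly + 2 later = 15. Adding the screening sample and the one-week safety blood count gives 15 + 2 = 17, the stated total. It is reached only with all twelve hourly draws.

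**2. Starts for which 6:30 pm is a true 12-hour draw.** Start = 18:30 minus elapsed time.
- 18:30 - 12 h 05 = 6:25 am
- 18:30 - 11 h 55 = 6:35 am

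**3. Starts for which 6:30 pm falls in the 11-hour window.**
- 18:30 - 11 h 05 = 7:25 am
- 18:30 - 10 h 55 = 7:35 am

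Starts between 6:35 and 7:25 am therefore put 6:30 pm between the two windows. Elapsed time then runs from 11 h 55 down to 11 h 05, which is 5 to 55 minutes short of 12 hours.

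**4. Elapsed time at 6:30 pm for assumed starts.**

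| Assumed start | Elapsed | Difference from 12 h |
|---|---|---|
| 6:00 am | 12 h 30 | +30 min |
| 6:30 am | 12 h 00 | 0 |
| 6:45 am | 11 h 45 | -15 min |
| 7:00 am | 11 h 30 | -30 min |
| 7:15 am | 11 h 15 | -45 min |
| 7:30 am | 11 h 00 | -60 min (same time as draw 11) |
| 8:00 am | 10 h 30 | -90 min (before draw 11) |

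**5. Are the earlier draws at risk?** The allowance names only the day's final draw. Other sections assume that all twelve are taken. Risks and Benefits speaks of twelve hourly draws through the catheter. Subject Compensation pays $10 per draw up to $120, and 120 / 10 = 12. The full payment also needs all twelve: 50 + 80 + 120 + 50 + 50 + 50 = $400, the stated amount for completing all visits. The 17-sample total in step 1 agrees. Together these support the reading that draws 1 to 11 stay in place and only the twelfth may move.

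**6. Size beside the tolerances already accepted.** A shift of 55 minutes is 55 / 720 = 7.6% of 12 hours. The allowance at 24 hours is 120 / 1,440 = 8.3%. The largest shift on this reading is thus no greater, in absolute or relative terms, than what the protocol accepts at the next point of the same curve.

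**7. Dose selection.** 18:30 - 8 h = 10:30 am, so an 8-hour draw falls due by 6:30 pm for any start up to 10:30 am. It keeps its own anchor to the start of infusion, and the allowance does not refer to it.

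**The case for a change.** The strongest case for a change is that the sampling schedule, its anchor and its window belong in the protocol. A draw cannot both be held to 12 hours +/- 5 minutes and be free to fall at a fixed clock time unless the start is fixed too. An assumed 7:00 am start misses by 30 minutes, six times the stated tolerance. The allowance has no bound, and one sentence would supply it at no cost in samples or visits.

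Part of this stands. The arithmetic is correct, and no start time or elapsed-time limit is given. The count of draws and the payment schedule support twelve draws but do not expressly limit the start time, and $120 is a maximum. The clock-time wording is looser than it need be.

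The charge of contradiction does not stand. A rule followed at once by a stated exception is not in conflict with it. The Data Analysis list omits the 5-minute and 2-hour tolerances as well, so it is a list of nominal times and cannot be read as excluding this one allowance. Whether an off-schedule sample is plotted at actual or nominal time is commonly left to the statistical analysis plan. The loss of earlier draws needs a late start combined with a use of the allowance that the rest of the protocol does not suggest.

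**Conclusion.** No change is needed. The sentence is a practical staffing allowance for one sample, and the gap it leaves is one that analysts fill by using the actual draw time.

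When the allowance is used and 6:30 pm falls between the 11-hour and 12-hour windows, the twelfth draw comes 5 to 55 minutes early. A start before 6:25 am would make it late instead (30 minutes for an assumed 6:00 am start). On the reading that draws 1 to 11 are kept, at most one of 15 Top2 time points per subject is touched, with eleven hourly points before it. That point serves a secondary objective, and the protocol attaches no test, threshold or decision to it. The dose is chosen on the 8-hour reading.

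This rests on three assumptions: the allowance moves only the twelfth draw, as the count of 17 and the payment schedule suggest; starts are early enough for the eleven earlier draws to be taken; and actual draw times are recorded. How often the allowance is used is not stated, so no overall share of affected samples can be given. Saying outright that only the twelfth draw may move would tidy the wording, but no conclusion of the trial depends on it.

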## **Study Population**

Subjects will be healthy females, ages 18 to 65 years. Up to 50 subjects will be screened in order to enroll up to 25 subjects.

Results from this protocol will be used to support future research with breast cancer patients; therefore, only women will be enrolled in the study. The protocol was approved by NIH review panel and program officer to study only female participants.

We plan to enroll 5 subjects to each of the 5 cohorts for a total of up to 25 subjects.

Participants will be recruited using the UAMS Translational Research Institute (TRI) Research Participant Registry, ARresearch.org. After the list of potential participants is obtained from TRI, we will contact the individuals via email, if indicated as their communication preference. The email we will use when communicating with potential participants is included in the IRB submission.

Participants will also be recruited using the Facebook pages of UAMS, TRI, and the Winthrop P. Rockefeller Cancer Institute. Participants may also be recruited at Community or University events, or from within UAMS via word of mouth.

Subjects will be asked to self-report on the inclusion/exclusion criteria. However, a baseline blood sample will be obtained to rule out anemia and pregnancy and to determine liver and kidney function.

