#### **Risks and Benefits**

Some subjects may experience discomforts, or pain on intravenous injection of dexrazoxane. We will minimize this risk by administering dexrazoxane as an IV infusion

over 15 (+/-5) minutes. If a participant reports pain during the infusion, the catheter will be checked to ensure it is properly inserted. If no problems are noted with the catheter, the rate of the infusion will be slowed. There is a very low probability that a subject may develop subcutaneous and cutaneous necrosis. Subjects will be informed and instructed to report to study team if she develops this side effect. PI and study team members will arrange for medical care and expect full recovery on this.

To reduce the risk of bruising and pain from multiple injections, the twelve hourly blood draws will be drawn from the IV catheter. If the initial IV line stops working for any reason, a new line will have to be placed.

There is a very low probability that a subject may develop myelosuppression. Each subject will have screening CBC one week after dextrazoxane infusion to rule out myelosuppression. The study team will arrange for medical care and expect recovery if a subject develops myelosuppression. If the one-week post-study blood counts are not within normal range, subject will have additional CBC at 2 weeks post-infusion.

The risk of allergic reaction is very low. In a rare situation, if the participant develops allergic reaction to dextrazoxane, the infusion will be stopped.

Other adverse events may include:

- Bluish color
- changes in skin color
- chest pain or tightness in the chest
- chills
- cold hands and feet
- cough, sneezing, sore throat
- difficult or labored breathing
- fever
- hoarseness
- lower back or side pain
- pain, redness, or swelling in the arm or leg
- painful or difficult urination
- swelling of the hands, ankles, feet, or lower legs
- tenderness
- unusual bleeding or bruising
- unusual tiredness or weakness)

All unanticipated problems or deviations should be reported immediately to principal investigator/sponsor. The immediate reports should be followed promptly by details written reports to investigator/sponsor. All reports will identify subjects by unique code numbers assigned rather than other identifiers. Unanticipated problems will be reported to IRB within 5 days of becoming aware of an event.

A risk to study participants is the potential for loss of confidentiality of study data.

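### Could a missed blood draw, or the reading of the 8-hour limit, decide which dexrazoxane dose is selected?

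*Protocol*

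**What the plan says.** The only numerical criterion for choosing a dose is in the Data Analysis section: "We will select a dose of dexrazoxane, which reduces Top2b to less than 5% of baseline level in 8 hours in 5 volunteers". The same section fixes the sampling, "The following time points will be assessed: Pre-infusion, 1, 2, 3, 4, 5, 6, 7, 8, 9, 10, 11, 12, 24, and 48 hours", counted from the start of infusion, and the cohort size, "Each dose level will be administered to up to five subjects".

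Study Design and Procedures also sets a ceiling and not a fixed number: "Our plan is to enroll up to 5 subjects per cohort". It describes the first step as starting at the lowest dose, to "analyze the Top2 protein level from up to five subjects". Study Population says: "We plan to enroll 5 subjects to each of the 5 cohorts for a total of up to 25 subjects".

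The paragraphs on visits and safety blood counts in Study Design and Procedures close with this sentence: "Treatment failure and subject removal criteria includes: subject noncompliance with blood draw, or, subject develops rare hypersensitivity reactions to dexrazoxane infusion". It does not say which of the two labels applies to which event, or how many missed draws amount to noncompliance.

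Four other places bear on the point:

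- Background and Rationale explains the 8-hour interval. Dexrazoxane is to be given eight hours before doxorubicin, so that Top2b is already degraded by then.
- Study Design and Procedures allows 5 minutes either side of each hourly draw.
- Risks and Benefits states that "the twelve hourly blood draws will be drawn from the IV catheter" and provides for a new line if the first one fails.
- Subject Compensation pays per draw and foresees partial completion.

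**The concern.** The rule names five volunteers and the cap is five, so there is no slack. If blood-draw noncompliance makes a volunteer a treatment failure, or removes her from the count, at most four responders remain and the literal rule cannot be met. That would hold even if she missed only the 24- or 48-hour draw and her 8-hour Top2b result was already in hand. A dose that works in everyone could be passed over for a reason unrelated to Top2b.

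The time limit in the rule can also be read in two ways: the level in the 8-hour sample, or a level below 5% in any sample up to 8 hours. The second reading gives eight chances to fall below the limit, so the same data could pass or fail.

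The selected dose is meant for a later randomized trial, so a loose criterion would carry forward.

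**Working it through.** **The protocol's own counts.** Cohorts: 5 × 5 = 25, as stated. Top2b time points: 1 pre-infusion + 12 hourly + 2 (24 and 48 hours) = 15. Adding the screening sample and the one-week blood count gives 17, the stated total. A rule on the 8-hour sample uses 2 of the 15 time points. Six (hours 9, 10, 11, 12, 24 and 48) come after it.

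**Missed draws, literal reading.** The protocol gives no loss rate, so r is assumed. For a dose that works in everyone, P(5 of 5) = (1 − r)^5:

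| r per volunteer | P(5 of 5) |
|---|---|
| 1% | 95% |
| 2% | 90% |
| 5% | 77% |
| 10% | 59% |

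Now take 1% infusion-day loss, with 2% or 5% of volunteers missing a return draw:

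- Any missed draw costs the volunteer: (0.99 × 0.98)^5 = 86%, or (0.99 × 0.95)^5 = 74%.
- Only the pre-infusion and 8-hour samples matter: 0.99^5 = 95%.

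**Does the text make that link?** The 86% and 74% need at least one of two things: that removal deletes results already obtained, or that a failure label overrides a measured 8-hour level below 5%. The protocol says neither. The dose rule is stated in Top2b level alone, and the term treatment failure does not appear in it. Specimen Handling and Storage discards samples only after they have been tested. Each volunteer has a single infusion of about 15 minutes, so removal after a missed later draw can only end further follow-up. The pre-infusion and 8-hour draws both fall in one supervised visit, and the hourly draws come from a catheter. With existing results kept, the same assumptions give 95%.

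**Reading of the 8-hour limit.** Assume a log assay error with SD s = 0.3 at each time, a baseline error shared within volunteer, no between-volunteer variation, and all five required to pass. For true residual R at hour 8:

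- 8-hour sample: P = Φ(ln(0.05/R)/(s√2))^5. For R = 6%, Φ(−0.430)^5 = 0.334^5 = 0.4%.
- Lowest of eight samples: the chance that at least one of the eight readings is below 5%, averaged over the baseline error, to the fifth power.

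| Chance that 5 of 5 pass | R = 6% | R = 8% |
|---|---|---|
| 8-hour sample | 0.4% | below 0.01% |
| Lowest of eight, exponential decline to hour 8 | 0.7% | 0.01% |
| Lowest of eight, plateau from hour 5 | 10% | 0.4% |
| Lowest of eight, flat from hour 1 | 25% | 1.8% |

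With s = 0.1 and R = 6%, the flat case falls to 0.6%. A separate simulation, with between-volunteer and assay CVs both 20% and a plateau at 2% from hour 4, gives 0.98 on the 8-hour sample and 1.00 on any sample. When suppression is deep and sustained, the reading hardly matters.

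**The case for a change.** The strongest reply is that this is the sole selection criterion for the primary objective, so its wording should be exact. Even if the failure heading is only a withdrawal list, removal alone leaves four where the rule names five. The two readings of the time limit can also differ sharply. In the simulation with 20% CVs, a fall to 3% at hour 4 with a rebound to 6% at hour 8 passes 0.2% of the time on the 8-hour sample and 83% on any sample. Nor does the rule say whether each of the five or their mean must be below 5%. With a plateau at 4%, the 8-hour criterion passes 23% of the time for each and 87% for the mean.

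Part of this stands. The joint heading is untidy, five and up to five do not match, and neither the time point nor the unit of the limit is spelled out. The consequences claimed do not follow from that:

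- Removal after hour 8 takes away no result.
- For a volunteer who lacks the 8-hour sample, Study Design and Procedures already foresees analysing fewer than five. The evidence is then thinner: the one-sided 95% lower bound on the response rate is 0.05^(1/4) = 47% for 4 of 4, against 0.05^(1/5) = 55% for 5 of 5. Who counts as evaluable, and how many are needed, is usual SAP content, and the SAP was not available for this point.
- No passage suggests a rebound before hour 8, and the stated reason for 8 hours is the level when doxorubicin would be given.
- A rule that counts volunteers is most naturally read as applying to each of them.

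**Conclusion.** No change to the plan follows. The missed-draw mechanism, which accounts for the drop from 95% to 86% or 74%, depends on a link between the removal sentence and the dose rule that the protocol does not make. On a sensible reading, a volunteer with pre-infusion and 8-hour results counts on those results, whatever later draws she misses. What is left of the missed-draw effect is loss on the infusion day, about 5% of cohorts at an assumed 1% per volunteer.

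The 8-hour limit is a gap in wording that the protocol's rationale and sampling schedule already fill in favour of the 8-hour sample, which is also the stricter reading. The alternative would raise false passes materially only for a true residual close to 5% with an early plateau or a rebound. With exponential decline, the difference at a 6% residual is 0.4% against 0.7%.

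All loss rates, assay errors and time courses here are assumptions, since the protocol gives none. The conclusion does not depend on their exact values. It rests on how the passages read together, and on evaluability rules being a matter for the SAP.
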